	Actual Behaviour change ^c	In response to receiving the air quality alert: 
 - I reduced length or level of my physical activity outdoors - I changed my travel route - I changed my exercise location - I changed the time when I travelled - I changed the time when I exercised outdoors - If you answered no, please report the reasons [text box].
	Medication adherence ^c	If you have lung problems: 
 - I used my preventer inhaler daily - I carried my reliever inhaler with me when going outdoors. - If you answered no, please report the reasons [text box].
Final Online Questionnaire – at 4 weeks	Behaviour change at 4 weeks ^b	- In the past 4 weeks, how often have you taken action to reduce exposure to air pollution, I response to hearing or reading an air quality forecast?
	Physical activity ^d	- To stay healthy, the NHS recommends at least 150 minutes of moderate physical activity (e.g. cycling, fast walking, swimming) every week (e.g. 30 minutes 5 days a week). Based on this, how physically active were you in the last week? ^e
	Action planning	
 - In the last 4 weeks, to reduce your exposure to air pollution, have you considered making permanent changes to your daily travel route or exercise place and time?^c - In the last 4 weeks, how often have you checked air quality information before doing physical activity outdoors?^b
	Worry ^a	Adapted from Witte et al. (34) 
 - The information received through the CityAir app made me worry about the possibility of suffering health effects from exposure to air pollution

	- The information received through the CityAir app made me nervous and tense about the possibility of suffering health effects from exposure to air pollution
Severity ^a	Adapted from Witte et al. (34)
	- Air pollution is a severe threat to my health
Conditional susceptibility ^f	- How likely do you think you are to suffer from health effects due to air pollution if you do not take any action to reduce exposure? - How likely do you think people of your same age and sex are to suffer from health effects due to air pollution if they do not take any action to reduce exposure?
Response efficacy ^a	Adapted from Witte et al. (34)
	- Following the health advice received through the CityAir app is effective in protecting me from exposure to air pollution

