Medication response efficacy ^a	If you have lung problems: - Taking my preventer medications daily is effective in helping me to control my asthma - Carrying my reliever medication with me is an effective way to protect my health
Self-efficacy ^a	Items adapted from Witte et al (34) and Rhode et al (35)
	- I am confident I would be able to follow the health advice received through the CityAir app, if I wanted to
Medication self-efficacy ^a	Items adapted from Witte et al (34) and Rhode et al (35)
	- If you have lung problems: I am confident I would be able to take my preventer inhaler every day , if I wanted to - I am confident I would be able to remember to carry my reliever inhaler with me during days of poor air quality, if I wanted to
Response costs ^a	- I do not have enough time to follow the health advice received through the CityAir app - Taking side roads makes my journey too long
Medication response costs ^a	If you have lung problems: - Using the preventer inhaler daily is not safe - Using the preventer inhaler daily makes me dependent on it
Unwanted consequences of intervention ^a	- In the last 4 weeks I stopped exercising altogether due to receiving alerts about poor air quality - In the last 4 weeks, I made an emergency /unplanned visit to A&E or visited my GP due to symptoms caused by air pollution
Sensory cue prevalence ^a	- I trust my own perception of air quality more than any official air quality alert
Credibility ^g	- Meyer's credibility index (36,37) (α=.67)
Clarity ^h	- Overall, how clear were the messages received?
Perceived informed choice ^a	- I received enough information to make an informed choice on how to reduce my exposure to air pollution
Intentions ^a to adopt protective behaviour in response to hypothetical, high air pollution alert	[After reading again the high air pollution hypothetical scenario and tailored advice] - I intend to follow the recommendations received with the air alert to reduce exposure to air pollution - I will avoid going outdoors - I intend to reduce length or level of my physical activity outdoors - I intend to change my travel route - I intend to change my exercise location - I intend to change the time when I travel - I intend to change the time when I exercise outdoors

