Medication adherence intentions ^a	If you have lung problems: - I intend to use my preventer inhaler daily - I intend to carry my reliever inhaler with me
Other intentions (not advised behaviours) ^a	- I will wear a mask as a protection from air pollution - I intend to reduce length or level of my physical exercise indoors

Notes: ^a Measured on 9-point scales, where 1=strongly disagree to 9=strongly agree; ^b From 1 Not at all to 9 all of the time; ^c Possible answers: yes, no, not sure; ^d From 1 Not at all, to 7 more than 150 minutes; ^e Possible answers: Low, Moderate, High, Very High, Not sure, I did not receive any alert; ^f From 1=not at all likely to 9=extremely likely; ^g on a 5-point scale; ^h 1= not clear at all to 9= extremely clear. Demographic data will be collected for all the participants in the first questionnaire.

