8 ETHICAL AND REGULATORY CONSIDERATIONS

8.1 Assessment and management of risk

As part of the study participants will be presented with one of two versions of health advice associated with real-time air quality notifications. All registered users who accept to take part in the study will receive real-time air quality notifications as usual. The control group will receive associated health advice in the usual format,

whilst the intervention group will receive advice in an alternative format. Which version of the advice they are given will be determined by random. Because we do not want to bias participants, we will not tell them exactly which parts have been changed. In line with the same need to avoid biasing participants, we will withhold one of the details of the hypothesis under test (i.e., that we want to specifically test whether the change in wording will have an impact on their intention and actual responses to the information received).

We have no reasons to believe that this may lead to any discomfort or known risks. However, to obviate any potential risk arising from this, we will provide a debriefing at the end of the study (via the online survey or via the app) and provide participants with all the researchers' contact details for doubts or concerns. The debriefing will explain the study hypotheses, methods and potential implications, and thank them for their contribution.

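### The two harm items are events recorded on a 9-point agreement scale, and Section 6.1 compares neither them nor week-4 physical activity between arms

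*Combined protocol and SAP*

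**What the plan says.** Table 4 in Section 5.6 has a row headed "Unwanted consequences of intervention ^a", asked only in the final questionnaire. It holds two statements: "In the last 4 weeks I stopped exercising altogether due to receiving alerts about poor air quality" and, for the same period, "I made an emergency /unplanned visit to A&E or visited my GP due to symptoms caused by air pollution". The marker a is defined under the table: "Measured on 9-point scales, where 1=strongly disagree to 9=strongly agree". For other past events, such as changing a route after a real alert or having used an inhaler, the table uses marker c: "Possible answers: yes, no, not sure".

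Physical activity ("how physically active were you in the last week") is asked in both the first and the final questionnaire, on a 7-point scale.

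Section 6.1 sets out the quantitative analyses. It names neither the two unwanted-consequence items nor physical activity as an outcome, and it gives no cut-off for counting an event on the 9-point scale.

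**The concern.** The investigators wrote these items to pick up adverse effects of the messages, but as planned the items can neither give an event rate nor enter an arm comparison. A score of 4 or 6 on a statement about having visited A&E has no clear meaning, and any threshold chosen later would be arbitrary.

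The omission matters because the efficacy outcomes can score giving up exercise as success. Reducing outdoor activity after an alert counts as a desired response, and the four-week outcome asks only how often the person acted to reduce exposure. The trial could report a benefit with no planned counterpart on harm. Any later comparison of these items would be unplanned, with the choice to report it made after the results are known.

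**Working it through.** **1. Response format.** Both harm items carry marker a (agreement, 1 to 9). Marker c (yes, no, not sure) is already used for real-alert behaviour and medication use. So 2 of 2 harm items use a scale that does not record occurrence, while a suitable format stands in the same table.

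**2. Analyses in Section 6.1.**

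| Planned analysis | Harm items or physical activity as outcome? | Related content that is compared by arm |
|---|---|---|
| ANCOVAs on intentions | No | Intention to avoid going outdoors; on a natural reading also the intention to cut indoor exercise |
| ANCOVAs on four-week behaviour | No | Frequency of action to reduce exposure |
| Chi-square tests after a real moderate episode | No | Reduced outdoor activity |
| Two-way MANOVA, closed list | No | Worry |
| Multiple regressions | No | None; the outcome is four-week behaviour |
| Mediation | No | None; limited to significant behavioural changes |

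The count is 0 of 6.

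**3. What the related measures can tell.** Take two runners in the enhanced arm. One moves the run to a park; the other stops running. Both can give the same high score on the four-week behaviour item, and each can answer yes to a desired response after a real alert. Worry and intentions are feelings and plans, not events. Within Table 4, the direct ways to tell the two runners apart are the first harm item and the physical activity item.

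**4. Message contrast (Section 5.5, Table 2).** Both arms advise some reduction in activity. At the moderate level the enhanced wording is broader. The usual message tells the general public to carry on as normal; the enhanced one says the same, then adds that exposure can be cut by doing less, or for less time, outdoors. For at-risk people the usual message asks those with symptoms to consider cutting strenuous activity; the enhanced one is not limited to symptoms or to strenuous activity. On the other side, enhanced messages suggest another route, place or time, and the high-level message for the general public says that staying indoors is not needed. The direction of the difference between arms cannot be settled from the text.

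**5. Precision of a yes/no comparison.** The plan gives no figure for harm. The one figure used from it is the minimum of 240 participants (Section 5.3). The event rates, 1:1 allocation and the number retained are my assumptions.

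- Retained: 240 × 0.8 = 192, or 96 per arm.
- 95% half-width = 1.96 × √[2p(1 − p)/n], with the same rate p in both arms.
- p = 0.05: 1.96 × √(0.095/96) = 1.96 × 0.0315 = 0.062, or 6.2 points.
- p = 0.10: 1.96 × √(0.18/96) = 1.96 × 0.0433 = 0.085, or 8.5 points.
- With 100 per arm (240/1.2 = 200 retained): 6.0 and 8.3 points. With 120 per arm (no loss): 5.5 and 7.6 points.

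At 5%, 96 per arm gives about 4.8 expected events (0.05 × 96), so these normal-approximation widths are only a guide.

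**6. Power of a test.** With 96 per arm, Fisher's exact test at 0.05 has power of about 9% for 2% versus 5%, 18% for 5% versus 10%, and 56% for 5% versus 15%. A test alone would say little.

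**The case against.** *The plan already looks at over-reaction.* This stands in part. Worry, the intention to avoid going outdoors and reduced outdoor activity are compared by arm. A reader might infer that the plan makes no comparison bearing on adverse reactions; that is too strong. The gap is confined to the two event items and physical activity.

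*The control messages also tell people to do less.* This stands. A reader might infer that the enhanced messages are the more harmful ones. The documents do not support that: the wording is broader at the moderate level but also carries alternatives to stopping.

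*Section 8.1 discounts risk.* A reader might cite "We have no reasons to believe that this may lead to any discomfort or known risks" as a claim that the messages are safe. In context it follows the explanation that participants will not be told which wording changed or one detail of the hypothesis, and debriefing is the remedy offered. It most naturally concerns that withholding, so it is no evidence here.

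*An agreement score can still be compared.* True: an ordinal shift between arms is analysable, so the scale alone does not make harm undetectable. But that comparison is not planned either, and it yields no event rate.

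*The fix will not detect rare harm.* This also stands, and it is why estimates with intervals are preferable to significance tests.

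*The scale rests on one table marker.* Markers in Table 4 are not fully reliable: the week-4 physical activity item also carries the marker for the alert-level answers. The investigators should confirm both scales, but marker a is the only one given for the harm items.

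**Conclusion.** The concern holds in a limited form. Two events labelled as unwanted consequences are recorded on a scale that gives no event rate, and neither they nor week-4 physical activity enters any of the six analyses in Section 6.1. The related measures that are compared do not separate adaptation from giving up exercise. The primary efficacy tests are unaffected. What is missing is the harm counterpart to any claim of benefit, so the change should be made.

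The absence of the comparison is read directly from the text and rests on no assumption. The precision figures (about ±6 points at a 5% event rate, ±8.5 at 10%) rest on assumed rates, 1:1 allocation and 96 per arm. The plan does not show that harm will occur, or in which arm.

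**What to change.** In Table 4, change the two items to the existing yes/no/not sure format, preferably with A&E and GP visits recorded separately. Confirm the response scale of the week-4 physical activity item.

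Add to Section 6.1:

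1. For each harm item, counts by arm and the risk difference with a 95% confidence interval suited to small counts, overall and descriptively in the at-risk group. State how answers of not sure are handled, and that a non-significant difference does not show absence of harm.
2. An ANCOVA of week-4 physical activity on arm, adjusted for baseline physical activity and target population.
3. A statement that both will be reported whatever the efficacy result.

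If the questionnaire has already launched, prespecify an ordinal comparison of the 9-point scores by arm, with the full distributions shown; item 2 is unchanged.

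The cost is two reworded items (three if the visits are split) and a few lines of analysis. Estimates will be imprecise, and splitting the visits makes each event rarer. Both items still ask respondents to judge the cause themselves, and the visit item attributes the visit to pollution rather than to the messages; the new format does not cure this. The harm items have no baseline counterpart, so their comparison cannot be adjusted for one.

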6. STATISTICAL ANALYSES

6.1 Quantitative data

ANCOVAs will be performed for all the intentions measures in relation to the high air pollution hypothetical scenario, adjusting for baseline measures collected about one month earlier (target population and intervention/control group entered as fixed factors). Both main and interaction effects will be tested. ANCOVAs will also be performed for the actual behaviour change at 4 weeks (with the intervention/control group entered as fixed factor). These latter analyses will also be ran in the subgroups of healthy and at-risk participants. Chi square tests will be performed to analyse differences in proportion of self-reported actual behaviour change between groups, in relation to a real moderate air pollution episode. A two-way MANOVA (1000 bootstraps) will test whether there are differences between groups (both main effects and interactions) in perceived susceptibility, worry, severity, perceived response efficacy, perception of time, self-efficacy, trust, clarity, credibility and perceived informed choice measures. Multiple linear regressions will be used to assess the associations between main predictor variables and self-reported behaviour change at 4 weeks. Mediations effects of predictor variables on significant behavioural changes will be tested using PROCESS macro (38).

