5. METHODS

5.1 DESIGN

This is a randomised control trial using a 2-way factorial design, with target population (2 levels: general population vs. individuals with a pre-existing health condition) and message format (2 levels: usual message format vs. behaviourally enhanced messages) as between-factors. Participants will be randomised to either the usual message group or the enhanced message.

[figure not shown]

Figure 2 Study flow diagram

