5.3 SAMPLE

Inclusion criteria

Inclusion:

- Users of air alert systems managed by the ERG
- Age: > 18 years
- Working or living in Greater London.

Exclusion criteria

- younger than 18 years
- not working or living in Greater London
- no longer users of the air quality alert smartphone application.

Sampling

Sample size was calculated using the G*Power statistical power analysis (32), to give 80% power to detect a statistically significant difference in the main outcome measures at $\alpha=0.05$, if a small to medium effect size of $f=0.02$ or higher is observed (9), adjusting for one covariate. Given the possibility of dropout, we inflated the sample size by 20%, and aimed to achieve a minimum sample size of $n=240$.

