For the purpose of the current study, KCL will launch an alternative version, which will allow the researchers to send different types of messages for the control and intervention groups during the study period. To increase message relevance, targeted advice will be sent to people with lung and/or heart or other existing condition, and the generally healthy public (see Table 3). It is worth noting that the current UK AQI does not provide targeted advice for people with heart conditions apart from reducing exertion, and the main advice for people with lung conditions is to consider using their reliever inhaler more often. Usually CityAir sends alerts for moderate, high and very high air pollution to users in the at-risk group, whilst sending only alerts for high and very high air pollution to users in the other groups. However, for the purpose of the current study, the alternative version of the application also will send moderate alerts and associated advice to the general population group. This will allow to actually test the UK AQI advice in case of a real moderate air pollution episode during the study period. To keep the study design simple, we will not differentiate between cyclists, joggers, and pedestrians. However, general messages also will include advice on how to adjust these types of physical activity to reduce exposure. Personal device IDs (i.e. an anonymous and unique identifier attributed to an individual mobile device) will be used to link

questionnaires completed at different time points by the same study participant. At the end of the study, a new version of CityAir will be issued to allow the application to go back to its usual functions.

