5.4.2 Recruitment and study procedure

All CityAir application users will be sent a notification about the current study containing a link to the participant information sheet. If eligible and happy to take part in the study, then they will be redirected to an online survey, using a well-known online platform (<https://www.surveymonkey.co.uk/>).

Once potential participants had agreed to take part, they will be asked to indicate whether they had a pre-existing health condition. Based on their answers, they will be divided into two groups (general public and at risk respondents). Respondents in both groups will be randomised via an algorithm run by CityAir to either a control or intervention condition.

Participants will be asked to read the scenario of a hypothetical high pollution episode and to indicate their intentions to follow the health advice given (i.e. baseline adherence intentions measure). After completion of the first questionnaire, all participants will be able to receive real-time CityAir notifications about real air pollution episodes. Whilst the control group will receive air quality notification and associated health advice in the usual UK AQI format, the intervention group will receive health advice in an alternative format (see Materials).

5.5 MATERIALS:

Table 2 shows the health advice accompanying air quality alerts in both the usual and alternative format (i.e. targeting message specificity). Table 3 shows some of the additional messages that will be sent to the intervention group and targeting specific psychosocial factors identified in our previous systematic review. Readability scores were calculated for all messages (using a readability tool available at: <https://www.webpagefx.com/tools/read-able/check.php>) and reported in Tables 2-3. To reduce the likelihood of confounding effects, the alternative messages have a similar word count and identical readability scores of 8 (i.e. they should be easily understood by 13 to 14 years old).

SHORT TITLE/ACRONYM: Improving the health impact of air quality alerts v.3

Table 2 The health advice associated with the current UK AQI compared with the alternative/more detailed health messages developed for this study.

Level of pollution	Usual messages of UK AQI*		Alternative messages (targeting message specificity)	
	General public	At risk	General public	At risk

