5.6 MEASURES

Table 4. Summary of measures.

Timing	Measure	How it will be measured
First Online Questionnaire – After reading hypothetical high air pollution scenario	Baseline intentions ^a to adopt protective behaviours in response to hypothetical, high air pollution alert	Assuming the situation described was happening right now, how much would you agree with the following statements? 
 - I intend to follow the recommendations received with the air alert to reduce exposure to air pollution - I will avoid going outdoors - I intend to reduce length or level of my physical activity outdoors - I intend to change my travel route - I intend to change my exercise location - I intend to change the time when I travel - I intend to change the time when I exercise outdoors
	Baseline medication adherence intentions ^a	If you have lung problems: 
 - I intend to use my preventer inhaler daily - I intend to carry my reliever inhaler with me
	Other baseline intention ^a (not advised behaviours)	
 - I will wear a mask as a protection from air pollution - I intend to reduce length or level of my physical exercise indoors
	Previous protective behaviour ^b	- In the past 4 weeks, how often have you taken action to reduce exposure to air pollution, I response to hearing or reading an air quality forecast?
	Planning	
 - In the last 4 weeks, to reduce your exposure to air pollution, have you considered making permanent changes to your daily travel route or exercise place and time?^c - In the last 4 weeks, how often have you checked air quality information before doing physical activity outdoors?^b
	Physical activity ^d	- To stay healthy, the NHS recommends at least 150 minutes of moderate physical activity (e.g. cycling, fast walking, swimming) every week (e.g. 30 minutes 5 days a week). Based on this, how physically active were you in the last week?
	Symptoms ^c	- Have you ever experienced symptoms caused by air pollution?
Air Alert period – Online questionnaires	Alert recall ^e	- Recently we sent you an air quality alert about poor air quality. What was the level of air pollution reported?

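### The ANCOVA for the primary 4-week behaviour outcome enters arm only and names no covariate, and its healthy and at-risk reruns have no interaction test

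*Combined protocol and SAP*

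**What the plan says.** Section 4 lists the effect of message format on behaviour at four weeks as primary question 2. Section 5.1 describes a "2-way factorial design, with target population (2 levels: general population vs. individuals with a pre-existing health condition") crossed with message format. Section 5.4.2 divides participants by health condition and then states: "Respondents in both groups will be randomised via an algorithm run by CityAir to either a control or intervention condition".

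Section 6.1 specifies two ANCOVAs in different detail:

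- **Intentions.** The model is fitted "adjusting for baseline measures collected about one month earlier", with target population and arm as fixed factors, and with main and interaction effects tested.
- **Behaviour at 4 weeks.** "ANCOVAs will also be performed for the actual behaviour change at 4 weeks (with the intervention/control group entered as fixed factor"). No covariate is named. The text continues: "These latter analyses will also be ran in the subgroups of healthy and at-risk participants".

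The only other interaction test in section 6.1 is in the MANOVA of perception measures, which does not include 4-week behaviour. Section 5.3 powers the main outcome measures "adjusting for one covariate" but does not say which one.

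In Table 4 (section 5.6) the previous protective behaviour item in the first questionnaire has the same wording and the same 1 to 9 scale as the 4-week outcome. It falls in a block whose timing reads "After reading hypothetical high air pollution scenario".

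**The concern.** Three things are left open or weak for a primary outcome.

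1. **Covariate.** The word ANCOVA and section 5.3 both imply one, but none is named. The first questionnaire offers several candidates: previous protective behaviour, planning, physical activity, symptoms and baseline intentions. The choice could be made after the data are seen. If the matching item is not the one used, precision is lost.

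2. **Population factor and interaction.** Participants are randomised within population groups and population is a design factor, yet the model ignores it. The question of whether the effect differs by population is left to two separate significance tests, which cannot answer it. The plan does not say whether those reruns are descriptive.

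3. **Timing of the matching item.** Section 5.4.2 describes randomisation before the hypothetical scenario, and Table 4 places the item after the scenario has been read. The item may therefore be answered after a randomised message has been seen, which would weaken its standing as a baseline covariate.

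**Working it through.** **Inputs.** From section 5.3: alpha 0.05, 80% power, one covariate, 20% inflation, minimum n = 240, printed f = 0.02. Assumed: f = 0.20, that is d = 2f = 0.40; N = 192 analysed (240 × 0.8); baseline-outcome correlations r of 0.3, 0.5 and 0.7; general/at-risk splits as shown.

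**The plan's own figure.** With f = 0.02, 80% power needs N = 19,625 before inflation, so 240 does not follow. With f = 0.20, N = 199, and 199 × 1.2 = 238.8, rounded up to 239, close to 240. That mismatch is a separate matter; it is the reason f = 0.20 is used here.

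**Method.** Noncentral F with 1 numerator df and noncentrality λ = N f². Arm only: λ = 192 × 0.04 = 7.68, power 78.7%. With 200 analysed (240/1.2): λ = 8.00, power 80.4%.

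**Covariate.** If f = 0.20 is on the unadjusted scale, adjustment gives λ/(1 − r²). If it is already on the adjusted scale, leaving the covariate out gives λ(1 − r²).

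| r | Unadjusted scale, with covariate: λ | Power | Adjusted scale, without covariate: λ | Power |
|---|---|---|---|---|
| 0.3 | 7.68/0.91 = 8.44 | 82.4% | 7.68 × 0.91 = 6.99 | 74.9% |
| 0.5 | 7.68/0.75 = 10.24 | 88.9% | 7.68 × 0.75 = 5.76 | 66.6% |
| 0.7 | 7.68/0.51 = 15.06 | 97.1% | 7.68 × 0.51 = 3.92 | 50.4% |

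The comparison figure is 78.7% in both cases. The true gain may sit at the low end: section 5.4.1 says "the alternative version of the application also will send moderate alerts and associated advice to the general population group", so the recall windows before and during the study differ for that group.

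**Population factor left out.** λ(1 − R²), where R² is the share of variance that population explains:

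- R² = 0.02: λ = 7.53, power 77.9%
- R² = 0.05: λ = 7.30, power 76.7%
- R² = 0.10: λ = 6.91, power 74.4%

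**Separate subgroup tests, identical true effect.** λ = 0.04n in each subgroup. P(exactly one significant) = p1(1 − p2) + p2(1 − p1).

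| Split | p1 | p2 | P(exactly one) |
|---|---|---|---|
| 96/96 | 0.492 | 0.492 | 0.500 |
| 134/58 | 0.632 | 0.322 | 0.547 |
| 144/48 | 0.664 | 0.274 | 0.574 |

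**Interaction test, 0.4 SD difference between populations.** λ = 0.16/[4(1/n1 + 1/n2)], divided by 1 − r² when the covariate is used.

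- 96/96: λ = 1.92, power 28%; at r = 0.5, λ = 2.56, power 36%
- 144/48: λ = 1.44, power 22%; at r = 0.5, λ = 1.92, power 28%

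**Arm effect taken from the interaction model with equal weights.** λ = 0.16/(1/n1 + 1/n2).

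- 134/58: λ = 6.48, power 71.6%
- 144/48: λ = 5.76, power 66.6%
- 154/38: λ = 4.88, power 59.4%

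A simulation (4,000 runs, 144/48, r = 0.5) agrees on the ordering: power was 89.2% for the main-effects model with the covariate and 79.0% for the equally weighted effect from the interaction model. The interaction test had type I error 5.1%.

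**The case against.** The strongest reply is that the covariate gap is one missing clause. Section 5.3 assumes a covariate, section 6.1 introduces the behaviour model directly after a baseline-adjusted one, and only one baseline item matches the outcome. On that reading baseline adjustment is intended, and the powers of 75%, 67% and 50% apply only if no covariate, or an uninformative one, were used. This is fair. The defect is an unnamed covariate, with other candidates available, in a primary model.

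Primary question 2 asks for a main effect, the plan does not say that subgroup results will be compared, and the proposed interaction test would seldom settle the matter. The low power stands. But the factorial design makes population a factor of interest, the reruns are not labelled descriptive, and discordant results would be common with no true difference.

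The figures rest on an f that the plan does not print. At f = 0.02, power is about 6% with or without a covariate (0.059 against 0.062 at r = 0.5). Section 5.3 can also be read as implying about 200 completers, which raises arm-only power to 80.4% and changes little else. The sizes are therefore conditional; the gaps in the text are not.

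The timing point rests on a table label that may cover the whole questionnaire, and the item asks about the previous four weeks. It is a possibility only, though cheap to remove.

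**Conclusion.** The concern holds. For primary question 2 the model contains arm alone, its covariate is unnamed, and population enters only through separate subgroup runs.

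The estimate is not biased by this. What is at stake is an analysis choice left open on a primary outcome, a loss of power if the matching item is not used (about 4 points at r = 0.3, 10 at r = 0.5 and 18 at r = 0.7, on the unadjusted-scale reading), and a 50% to 57% chance of discordant subgroup results when the true effects are equal. The missing population factor matters least.

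These sizes depend on f = 0.20, 192 analysed, and the assumed correlations and splits. The plan should be changed, but the trial's validity is not threatened.

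**What to change.** In section 6.1:

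1. Test the arm effect on 4-week behaviour in an ANCOVA with arm and target population as fixed factors, no interaction term, and the baseline previous protective behaviour score as the named covariate.
2. Add arm × population in a second model, stated to be supporting and of low power.
3. Report the general-population and at-risk effects with confidence intervals from that second model, labelled descriptive, in place of separate significance tests.
4. Do not take the primary arm effect from the interaction model with equal weights, because unequal groups would reduce its power.

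In the first questionnaire, ask the previous protective behaviour item before any randomised message is shown.

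The cost is two or three sentences, one extra model and one moved question, with no new data. The drawback is that the interaction test will rarely be conclusive, and the plan should say so.
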